5 STUDY OBJECTIVES

5.1 PRIMARY

To evaluate, in comparison with placebo, the efficacy of SAR156597 administered subcutaneously for 24 weeks on skin fibrosis in patients with dcSSc.

5.2 SECONDARY

- To evaluate the efficacy of SAR156597 compared to placebo on physical/functional disability in patients with dcSSc.
- To evaluate the efficacy of SAR156597 compared to placebo on respiratory function of patients with dcSSc.
- To evaluate the safety profile of SAR156597 compared to placebo in patients with dcSSc.
- To evaluate the potential for immunogenicity (ADA response) of SAR156597 in patients with dcSSc.
- To evaluate the PK (trough plasma concentrations) of SAR156597 administered subcutaneously for 24 weeks.

5.3 EXPLORATORY

- To explore the efficacy of SAR156597 compared to placebo on other manifestations of SSc (gastrointestinal, joint pain, cardiovascular and renal manifestations) in patients with dcSSc.
- To explore the effect of SAR156597 on the Quality Of Life in patients with dcSSc.
- To measure the effect of SAR156597 on biomarkers of the disease activity and the IL-4/IL-13 pathway.

6 STUDY DESIGN

6.1 DESCRIPTION OF THE STUDY

This study will be a multinational, randomized, double-blind, placebo-controlled, 2 parallel groups, proof of concept Phase 2 study to assess the efficacy and safety of SAR156597 200 mg administered subcutaneously once a week over a 24 week period to patients with diffuse SSc. Approximately 94 patients will be randomized in a ratio 1:1 to the following two treatment groups:

- SAR156597 group (n = 47): Patients will receive SAR156597 administered subcutaneously in 200 mg doses qw
- Placebo group (n = 47): Patients will receive placebo subcutaneously qw.

Randomization will be stratified based upon the patients' medical history of SSc-ILD (yes or no).

For a schematic presentation and a detailed flow chart, please refer to [Section 1.2](#).

6.2 DURATION OF STUDY PARTICIPATION

6.2.1 Duration of study participation for each patient

The study can last up to 39 weeks as follows:

- 4 weeks of screening
- 24 weeks of study treatment
- 11 weeks of follow-up with no study treatment.

6.2.2 Determination of end of clinical trial (all patients)

The end of the clinical trial is defined as the day the last patient completes his/her last visit planned in the protocol.

6.3 INTERIM ANALYSIS

A futility analysis will be conducted, if needed. A two-step analysis will be performed. Please refer to [Section 11.5](#).

6.4 STUDY COMMITTEES

Data Monitoring Committee

A Data Monitoring Committee (DMC) will be charged with monitoring the safety of the patients participating in this clinical trial. This committee is comprised of externally-based individuals with expertise in the diseases under study, biostatistics, or clinical research. The DMC will, in due time, give appropriate recommendations to the Sponsor on safety aspects during the conduct of the study, if needed. The DMC is justified by the early stage of development of SAR156597 in patients with SSc. The DMC responsibilities and the data review processes are fully described in the DMC charter. In the above capacities, the DMC is advisory to the Sponsor. The Sponsor is responsible for promptly reviewing and for taking into account in a timely manner the recommendations of the DMC in terms of trial continuation with or without alterations or of potential trial termination.

7 SELECTION OF PATIENTS

7.1 INCLUSION CRITERIA

- I 01. Systemic Sclerosis according to the ACR/EULAR 2013 criteria (8).
- I 02. Diffuse cutaneous form of SSc according to Leroy's criteria.
- I 03. Able and willing to sign the written informed consent form with comprehension of its contents and comply with the requirements of the study protocol.

7.2 EXCLUSION CRITERIA

- E 01. Age <18 years of age.
- E 02. Disease duration of >36 months from time of first non-Raynaud's phenomenon manifestation.
- E 03. mRSS <10 or >35 at screening and baseline visits.
- E 04. History of vasculitis, active or in remission.
- E 05. Diagnosis of connective tissue disease (other than SSc) or overlap syndrome (eg, polymyositis/SSc).
- E 06. Positive Human Immunodeficiency Virus (HIV) serology or a known history of HIV infection, active or in remission.
- E 07. Abnormal hepatitis B and/or hepatitis C tests indicative of active or chronic infection:
 - Abnormal Hepatitis B tests: Positive hepatitis B surface antigen (HBsAg) OR positive total hepatitis B core antibody (HBcAb) with negative hepatitis B surface antibody (HBsAb) OR positive total HBcAb with positive HBsAb and presence of hepatitis B DNA (HBV DNA).
 - Abnormal Hepatitis C tests: Positive anti-hepatitis C virus antibody (HCV Ab) and positive HCV RNA.
- E 08. Positive or 2 confirmed indeterminate Quantiferon-TB Gold tests at screening (regardless of prior treatment status).
- E 09. Serious infection (eg, pneumonia, pyelonephritis) within 4 weeks of screening, infection requiring hospitalization or intravenous antibiotics within 4 weeks of screening or chronic bacterial infection (eg, osteomyelitis).
- E 10. History of anaphylaxis to any biologic therapy.

- E 11. Evidence of any clinically significant, severe or unstable, acute or chronically progressive, uncontrolled infection or medical condition (eg, cerebral, cardiac, pulmonary, renal, hepatic, gastrointestinal or neurologic other than SSc or SSc-ILD) or previous, active or pending surgical disorder, or any condition that may affect patient safety in the judgment of the investigator.
- E 12. At screening, the % predicted forced vital capacity (FVC) is $\leq 75\%$ AND % predicted carbon monoxide diffusing lung capacity (DLCO) after hemoglobin correction is $\leq 40\%$
- E 13. History of heart failure (including acutely decompensated in the setting of preserved ejection fraction), Left Ventricular Ejection Fraction (LVEF) $\leq 45\%$, coronary artery disease, angina, myocardial infarction, ischemic cardiomyopathy and/or hypertrophic cardiomyopathy
- E 14. Any prior history of malignancy or active malignancy, including lymphoproliferative diseases (except successfully-treated carcinoma in-situ of the cervix, non-metastatic squamous cell or basal cell carcinoma of the skin) within 5 years prior to baseline.
- E 15. Ischemic ECG changes (except those NOT supported by the findings of a left heart catheterization performed in the last year within screening) and/or other clinically significant ECG findings ([Appendix L](#)) at screening. (All abnormal ECG finding will be reviewed and confirmed by a local cardiologist.)
- E 16. High dose steroids (>10 mg/day prednisone equivalent); or a change in steroid dose within 4 weeks prior to randomization (or baseline visit); or expected changes during the course of the study.
- E 17. Previous treatment with rituximab within 12 months prior to screening.
- E 18. Previous treatment with bone marrow transplantation, total lymphoid irradiation or ablative ultra-high dose cyclophosphamide.
- E 19. Treatment with high dose immunosuppressive drug (eg, cyclophosphamide >1 mg/kg oral/day or >750 mg IV/month; azathioprine >100 mg/day; methotrexate >15 mg/week; mycophenolate mofetil >2 g/day) within 3 months of screening or a change in dose within 4 weeks prior to randomization (or baseline visit); or expected changes in dose during the course of the study.
- E 20. Treatment with etanercept, cyclosporine A, intravenous immunoglobulin (IVIG), rapamycin, D-penicillamine, tyrosine kinase inhibitors within 4 weeks of screening or antithymocyte globulin within 6 months of screening.
- E 21. Treatment with infliximab, certolizumab, golimumab, abatacept, or adalimumab, tocilizumab within 8 weeks of screening or anakinra within 1 week of screening.
- E 22. Treatment with any investigational drug within 1 month of screening, or 5 half-lives, if known (whichever is longer).

E 23. Abnormal laboratory test(s) at screening:

- Alanine transaminase (ALT) or aspartate transaminase (AST) >2 times upper limit of normal range (ULN)
- Hemoglobin <11 g/100 mL for male and <10 g/100 mL for female
- Neutrophils <1500/mm³ (except <1000/mm³ for those of African descent)
- Platelets <100 000/mm³
- Creatinine \geq 150 μ mol/L.

Note: Laboratory parameters may be repeated once during the screening period if felt to be spurious or due to technical error in order to determine eligibility.

E 24. Current history of substance and/or alcohol abuse

E 25. Current employee of Sanofi or has an immediate family member (eg, spouse, parents, child or sibling) who is a current employee of Sanofi.

E 26. Currently incarcerated or anticipated/scheduled to be incarcerated during the course of the study.

E 27. Any condition or circumstance that will preclude the patient from following and completing protocol requirements, in the opinion of the Investigator.

E 28. Pregnant or breastfeeding woman

E 29. Women who are of childbearing potential not protected by highly-effective contraceptive method(s) of birth control (defined in the informed consent form and/or [Appendix G](#) for United Kingdom), and/or who are unwilling or unable to be tested for pregnancy.

Note: Women of childbearing potential must have a confirmed negative pregnancy test at screening and randomization visits. They must use an effective contraceptive method throughout the entire duration of the study treatment, and for at least 12 weeks after the last administration of IMP. Postmenopausal women must be amenorrheic for at least 12 months.

8 STUDY TREATMENTS

8.1 INVESTIGATIONAL MEDICINAL PRODUCTS

A complete description of the IMP and its proper handling will be provided in a pharmacy manual.

8.1.1 Pharmaceutical Form

- SAR156597 solution for injection at 100 mg/mL: SAR156597 is supplied as a sterile freeze-dried powder for solution for injection, in a glass vial. Each vial is filled with 125 mg of SAR156597 freeze-dried powder, and the final solution for injection is obtained by reconstitution of the entire vial content with 1.1 mL of sterile water for injection, leading to an amount of 125 mg of SAR156597 drug substance in a total volume of 1.25 mL equating to a concentration of 100 mg/mL of SAR156597 solution. One (1) mL of this 100 mg/mL SAR156597 solution can then be withdrawn for dose administration. Two (2) drug product vials are thus needed to reach a 200 mg dose and to prepare a 2 mL SAR156597 solution syringe.
- Placebo in lyophilized form: each vial containing excipients, is to be reconstituted with 1.1 mL of sterile water resulting in a total volume of 1.25 mL. Two (2) placebo product vials are required with 1 mL to be taken from each vial to prepare a 2 mL placebo solution syringe.

8.1.2 Dose of drug per administration

- SAR156597 group: 1 injection of SAR156597 200 mg administered subcutaneously qw.
- Placebo group: 1 injection of placebo administered subcutaneously qw.

8.1.3 Method of preparation

The SAR156597 and the placebo must be reconstituted prior to injection. The description of the reconstitution from lyophilizate vials will be provided in a pharmacy manual.

Once reconstituted, the placebo and the active vials are subtlety distinguishable. Thus, in order to maintain blinding at the study site, the reconstitution of the IMP and the preparation of the syringe must be done by an unmasked personnel (eg, pharmacist) other than those administering the drug and making clinical observations (Refer to [Section 8.3](#)).

At the patient's home, reconstitution must be prepared and administered by healthcare professionals (eg, visiting nurse).

The IMP should be reconstituted the day of dosing (no more than 3 hours prior to SC injection), at room temperature.

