- l* In women of child-bearing potential. After Visit 6 (W12) and until subsequent study visit the patient will have a urine pregnancy test at home on a monthly basis. Patients will be given sufficient urine pregnancy kits to take home for monthly testing up until the end-of-study visit. When the testing coincides with a study visit as indicated in the flow chart, the results should be reported in the e-CRF. When the testing is done at home between study visits, the results should be collected by the Investigator during the monthly phone calls (Week 16 and Week 20) and reported in the electronic case report form (e-CRF). If any interim urine pregnancy test performed by the patient is positive, the patient should immediately report to the investigator for appropriate follow-up and pregnancy reporting as appropriate
- m* Local tolerability of SC injections will be assessed by the study nurse either at patient's place or at the site for the inter-visit SC injection given once a week. One patient booklet to record information on injections administered at home will be provided to the patient at baseline and will be reviewed at each visit by Investigator
- n* Step 1 of CRISS will be assessed based upon available data and individual components of Step 2 of CRISS will be captured through other efficacy procedures (eg, Change in mRSS, HAQ-DI, patient and physician global assessments and FVC)
- o* This will be assessed using a Likert scale for CRISS calculations and will be a separate assessment from the global assessment conducted for the SHAQ using a VAS.
- p* This will be assessed using a Likert scale for CRISS calculations.
- q* Health care resources will include hospitalizations (reason, number of days per hospital admission, date of entry, date of discharge from hospital), number of out-patients visits by type (gastroenterologist, pulmonologist, occupational therapist, psychiatrist, physiotherapist, other), sick leaves (number of day off from work) and caregiver support (time spent per day to take care of the patient, number of days off from work to take care of the patient)
- r* An additional IVRS call will need to be made at Week 18 for IMP dispensation. Only 6 weeks of IMP will be dispensed with the IVRS call made at Visit 6 (W12)

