8.1.4 Route and method of administration

The route and method of administration are SC in the abdomen. SC injection sites should be alternated between the 4 quadrants of the abdomen (avoiding navel and waist areas) so that the same site is not injected for two consecutive weeks. The exact site of each injection will be documented on the source document. It is recommended that the injection occur at a site free of SSc involvement, if possible.

The IMP is administered every 7 days ± 2 days from initial IMP administration. This window is permitted per protocol to accommodate various circumstances (eg, pending laboratory results, management of AE, visit scheduling difficulty). The IMP administration should be performed by other site personnel, blinded from the person in charge of the preparation of the solutions and syringes.

If IMP administration is missed or temporarily discontinued, the initial schedule of injections may be resumed upon the investigator's medical judgment and discretion while the missed dose(s) will not be administered. This does not apply to permanent treatment discontinuation.

On days when the patient has a study visit, the IMP will be administered by the Investigator or delegate after clinic procedures and blood collection.

For doses not administered at the study site, the IMP will be administered by qualified site personnel and /or healthcare professionals (eg, visiting nurse service).

Patients should be monitored by site personnel/visiting nurse for at least 30 minutes or up to 2 hours as per country specific requirements after each administration for potential signs and symptoms that may suggest a hypersensitivity reaction.

For doses not given at the study site, a booklet will be provided to the patient to record information related to the injections; this booklet will be completed by the visiting nurse after each injection and will be kept as source data in the patient's study file. Patients will be instructed to bring the booklet back at the subsequent site visit for Investigator's review.

Between the protocol-scheduled on-site visits, interim visits to the site may be required for IMP dispensing. As an alternative to these visits, the IMP may be supplied from the site to the patient via a Sponsor-approved courier company where allowed by local regulations and approved by the patient.

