8.3 BLINDING PROCEDURES

8.3.1 Methods of blinding

SAR156597 and placebo will be provided in treatment kits indistinguishable in appearance and will be labeled with a treatment kit number. The list of treatment kit numbers will be generated by Sanofi. A patient randomization list will be generated by the interactive voice response system (IVRS). Both the randomization and treatment kit lists will be loaded into IVRS.

In accordance with the double-blind design, study patients, Investigators, and study site personnel (except the personnel who conduct the reconstitution of the IMP and preparation of syringes for injection) will remain blinded to study treatment and will not have access to the randomization code except under circumstances described in [Section 8.3.2](#).

Before the reconstitution, the lyophilized SAR156597 and lyophilized placebo are similar. Once reconstituted, the active solution differs subtly in its appearance from the placebo solution. In order to maintain blinding conditions, the personnel involved with dose and syringe preparation will be required not to reveal to other study personnel the type or characteristics of IMP solution (SAR156597 versus placebo) in the vials and syringes.

Please refer to [Section 10.4](#) for unblinding by the Sponsor related to suspected unexpected serious adverse drug reaction.

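### Home dosing has no preparer–observer separation and no syringe masking, although the reconstituted solutions are distinguishable; up to 19 of 24 doses are open to this

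*Protocol*

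**What the plan says.** Protocol 8.1.3 gives the premise: "Once reconstituted, the placebo and the active vials are subtlety distinguishable". Section 8.3.1 repeats it: "Once reconstituted, the active solution differs subtly in its appearance from the placebo solution".

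For the site, 8.1.3 draws the consequence. With the stated purpose "in order to maintain blinding at the study site", preparation "must be done by an unmasked personnel (eg, pharmacist) other than those administering the drug and making clinical observations". Section 8.1.4 adds: "The IMP administration should be performed by other site personnel, blinded from the person in charge of the preparation of the solutions and syringes".

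For the patient's home, 8.1.3 has a single sentence: "reconstitution must be prepared and administered by healthcare professionals", with a visiting nurse as the example. Neither it nor 8.1.4 asks for a second person or a masked syringe at home.

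Three other places bear on the home dose:

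- Flow chart note m, on injections between visits: "Local tolerability of SC injections will be assessed by the study nurse", at home or at the site.
- Section 8.1.4 has the visiting nurse complete the booklet after each injection given away from the site. The booklet is kept as source data.
- Section 8.3.1 keeps patients, investigators and site personnel blinded but exempts those who reconstitute. It forbids preparers to disclose what they saw to colleagues on the study; it does not mention the patient.

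Section 8.7.1 makes home dosing a patient option, where local law allows it.

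**The concern.** The protocol treats the visible difference between the solutions as large enough to need two people at the site. The difference is the same at home, yet the safeguard is absent there and nothing replaces it. A nurse who has reconstituted the vials may have seen a cue to the allocation, and may then grade the injection site and write the record used as source data.

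Two things are exposed. The first is injection-site tolerability, which the protocol synopsis lists under safety. Severe injection-site reactions are an adverse event of special interest (10.4.1.3), and severe local skin reactions appear among the discontinuation events (10.3.3), so the ratings have consequences. The second is the patient's own blinding. If the patient sees or is told something about the solution, patient-reported outcomes could be affected, including HAQ-DI, a secondary endpoint.

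**Working it through.** **Who may do what.** Setting the sections side by side:

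| Task | At the site | At home |
|---|---|---|
| Reconstitute and fill syringe | Unmasked preparer (8.1.3) | Visiting nurse permitted (8.1.3) |
| Inject | Someone else, blinded (8.1.3, 8.1.4) | Same nurse permitted (8.1.3) |
| Rate local tolerability | Not the preparer (8.1.3) | Nurse (note m) |
| Write the record | Site staff | Visiting nurse, in the booklet (8.1.4) |
| Duty of silence | Towards study staff (8.3.1) | The same; nothing said about the patient |

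Nothing stops one person from holding every task in the right-hand column. A rule against telling colleagues cannot help when the preparer is also the observer.

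**How many doses.** The documents give no number of home doses, so it is counted from the visit schedule.

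- Dosing is weekly from Day 1 (Week 0), with the last dose at Week 23: 24 doses.
- Treatment-period site visits are at Day 1 and Weeks 2, 4, 8, 12 and 24. Week 24 carries no dose, so doses on site visits = 5.
- Doses between visits = 24 − 5 = 19, and 19/24 = 79%.

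The dispensing instructions in 10.1.2 to 10.1.7 give the same count:

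| Kits allocated at | Dose at the visit | Doses between visits |
|---|---|---|
| Day 1 | Week 0 | Week 1 (1) |
| Week 2 | Week 2 | Week 3 (1) |
| Week 4 | Week 4 | Weeks 5–7 (3) |
| Week 8 | Week 8 | Weeks 9–11 (3) |
| Week 12 | Week 12 | Weeks 13–17 (5) |
| Week 18 (IVRS call, no visit) | none | Weeks 18–23 (6) |
| Total | 5 | 19 |

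Kits: 2 + 2 + 4 + 4 + 6 + 6 = 24. Between visits: 1 + 1 + 3 + 3 + 5 + 6 = 19.

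**Scale across the trial.** With 94 patients the ceiling is 94 × 19 = 1,786 of 94 × 24 = 2,256 doses. Uptake of home dosing is not stated. If a share *h* of patients take every between-visit dose at home, the exposed share of all doses is *h* × 19/24. As assumptions only: *h* = 25% gives 20%, *h* = 50% gives 40%, *h* = 100% gives 79%.

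**Timing.** Of the 19 between-visit doses, 8 fall in Weeks 1 to 11 and 11 in Weeks 13 to 23. All scheduled on-site doses are at or before Week 12, so dosing setting is confounded with time on treatment.

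**What the SAP does with the ratings.** SAP 2.1.5 to 2.1.5.5 and 2.4.5 specify no local-tolerability table. The only specific item is severe injection-site reactions as an adverse event of special interest (2.1.5.1). Nothing separates home from site ratings, so a rater effect would not be visible.

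**The case against.** The case on the other side is substantial, and much of it stands.

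- **No rule is literally broken.** A reader might infer that home dosing violates the protocol's own blinding rule. The text does not support that. The separation sentence in 8.1.3 is limited to the study site, 8.1.4 speaks of site personnel, and 8.3.1 exempts preparers from blinding. This is a gap: the stated reason applies at home and the rule does not follow it there.
- **The patient is not said to watch.** A reader might picture reconstitution in front of the patient. No section says where it takes place. The protocol permits it and does not describe it.
- **Distinguishable is not identified.** Kits look alike, the powders are similar, and the solutions differ only subtly. In a parallel-group trial a patient sees one product and has no comparator, and a nurse with one patient may have none either. This lowers the probability of unblinding. It does not remove it, since the sponsor judged the same difference worth separating staff over at the site.
- **The HAQ-DI route is indirect.** Section 10.1 has questionnaires completed at the site, in general before substantive contact with health professionals, and secondary p-values are descriptive (11.4.2.3). This stands.
- **Tolerability is descriptive and partly measured.** No safety hypothesis is tested, and Appendix J grades erythema and swelling largely by diameter. Pain, tenderness and itching depend more on judgement.
- **The pharmacy manual was not available.** It may already contain masking or home-preparation instructions.

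None of this answers the basic point that the protocol sets no blinding safeguard specific to home dosing.

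**Conclusion.** The gap is real and modest in consequence. For up to 19 of 24 doses (79%), one visiting nurse may prepare a distinguishable solution, inject it, rate the injection site and write the source record. The figure is a maximum: home dosing depends on patient choice and local law, and between-visit doses may also be given and assessed at the site.

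The direct effect is confined to injection-site tolerability and related observations at home. Patient-reported outcomes are affected only if the patient learns the allocation. It would be tempting to extend the concern to the primary result. The documents do not support that: mRSS is rated at site visits by trained personnel (9.1.4.1), so it would be reached only if the nurse's knowledge passed to the patient or the site.

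The conclusion assumes that the appearance difference can carry information to the person who reconstitutes, and that no unseen manual already closes the gap. It supports a cheap improvement and does not call the trial's main inference into question.

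**What to change.** In the protocol and pharmacy manual:

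1. Reconcile 8.1.3, 8.1.4, 8.3.1 and flow chart note m so that they say explicitly how blinding is kept for home doses.
2. Require home reconstitution out of the patient's sight, and an opaque sleeve or label on the filled syringe in both arms.
3. Extend the non-disclosure duty in 8.3.1 by name to the visiting nurse, towards both the patient and the site.

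Optionally, in the SAP: add a descriptive summary of local tolerability by arm and dosing setting. This is a new table, since none exists to split. It should state that setting is confounded with time; restricting one panel to doses up to Week 12 would make the settings more comparable (5 scheduled on-site doses against 8 between visits). It can still be done after dosing ends, provided the setting of each injection was recorded.

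The cost is manual text, sleeves and perhaps one table, with no added staff. The limit is that these measures protect the patient's and the site's blinding, not the nurse's. A sleeve cannot mask a syringe from the person who filled it, so home tolerability ratings should be reported as coming from a potentially unmasked rater.
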